
Duration of Subject Participation
	
The total study duration for each subject will be either 33–36 weeks or 58-61 weeks, including and depending on:
 
 • Screening period of 14–60 days (or a maximum of 35 days after the Screening EGD, whichever is shorter) prior to study drug administration.

Duration of Subject Participation cont.
	
 • Treatment period of 24 weeks (± 3 days) beginning the day of the first dose and ending 4 weeks after the last dose. • Optional Open-Label Extended Dosing Period of 28 weeks (± 3 days), or Follow-up period of 4 weeks (± 3 days). 
Regardless of whether a subject participates in the OLE period or not, all subjects will be followed for 8 weeks after the last dose of study drug. If lymphocyte or eosinophil counts have not recovered by Day 197 or Day 372 for subjects participating in the OLE period, subjects will return every 28 days for extended follow-up until counts have recovered.

Safety Evaluations
	
Safety and tolerability will be assessed throughout the study by monitoring and evaluating AE, including any complications resulting from the intravenous infusion. All TEAE will be collected from the start of study drug administration through Day 197 (± 3 days) or Day 372 (for subjects participating in the OLE period) or Early Termination.
 
Severity of AE will be assessed using the National Cancer Institute Common Terminology Criteria for Adverse Events (Version 5.0 or most current version). All AE will be assigned a severity grade and will be assessed for clinical significance and relationship to study drug.
 
Additional safety evaluations include clinical laboratory tests, including anti-drug antibody to AK002, complete blood counts, chemistries, and urinalyses as well as physical exams and vital signs measurements.
 
The Medical Monitor will review blinded safety data throughout the study. The safety monitor will review blinded safety data and escalate to the Medical Monitor as appropriate.
 
An independent Data Monitoring Committee (iDMC) has been convened and will meet at regularly scheduled intervals in accordance with the iDMC charter.
 
During the period of extended follow-up, data collection will be limited to hematology, serious adverse events, and adverse events of special interest.

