- 28) The day before the first dose (12–24 hours prior to the planned infusion start time), eligible subjects will self-administer oral prednisone premedication based on body weight.
- 29) Study drug (or placebo) will be administered as a single peripheral IV infusion over ≥ 4 hours on Day 1, over ≥ 3 hours on Day 29, and over ≥ 2 hours for subsequent infusions (Days 57, 85, 113, and 141). Refer to the Pharmacy Manual for detailed instructions on preparation, administration, and infusion rate schedule requirements.
- 30) If a new or worsening symptom (or clinically significant finding) is observed or reported, the Investigator or designee will perform a symptom-directed physical examination. Symptom-directed physical examinations will be performed as needed and may be performed predose, during infusion, and/or postdose (including for possible IRRs).
- 31) All AE, including Adverse Events of Special Interest (AESI) and SAE, will be captured beginning from the start of the first infusion. Serious adverse events occurring between the time of consent and the start of the first study drug infusion will be reported only if they are assessed to be related to study procedures. For subjects participating in the OLE period, AE will be assessed and recorded in the CRF of the AK002-014 treatment period database up until the start of the first open-label infusion during the Day 176 visit and recorded in the CRF of the AK002-014 OLE period database beginning from the start of the first open-label infusion during the Day 176 visit.
- 32) ET visits should be conducted 28 (± 3) days after the last dose of study drug or prior to this, if necessary, to ensure compliance with the visit. If a subject discontinues the study > 28 days after the last dose of study drug, the ET visit should be conducted as soon as possible. If the subject is terminated after Day 29 and before Day 169, the ET visit will be performed 28 (± 3) days after last dose and the ET visit will follow the Day 169 assessment schedule (including EGD with biopsy collection). If the subject is not participating in the OLE period and the ET visit occurs after Day 169, the Day 197 assessment schedule should be followed for the ET visit. See [Table 5](#) OLE Period Schedule of Events for OLE period ET after Day 176.

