11.2.8 Complete Blood Count with Differential

Blood for CBC with differential will be obtained at all study visits. On dosing days (Days 1, 29, 57, 85, 113, and 141), blood for CBC with differential will be drawn twice: predose and 1 hour postdose.

The blood sample will be processed and shipped in accordance with the central laboratory manual and lab kit instructions. The central laboratory will analyze the blood sample and provide results for CBC with differential, including hemoglobin, hematocrit, platelet count, red blood cell count, white blood cell count, and absolute differential count (neutrophils, lymphocytes, monocytes, eosinophils, and basophils).

As described in the Investigator's Brochure, expected effects of AK002 include changes in absolute lymphocyte and eosinophil counts, so these results could potentially unblind the blinded members of the study. Consequently, with the exception of screening and Day 1 predose, the CBC differential results (neutrophils, lymphocytes, monocytes, eosinophils, and basophils) will be blinded to both the Sponsor and the study site. The CBC differential results for Day 1 (1 hour postdose), Days 8, 15, 29, 57, 85, 113, 141, 169, and 197 (or ET) will therefore be unavailable during the study and will not be provided to the Sponsor or study site until after final database lock and unblinding.

The Safety Monitor will have real-time access to these laboratory results and will review and escalate any concerns/issues to the Medical Monitor and/or the site as appropriate. An unscheduled CBC, with differential may be collected if requested by the Safety Monitor. All panic alerts for blinded values will be sent to the Safety Monitor and evaluated in real time.

If the CBC differential results from Day 197 (or ET) show that absolute lymphocyte and/or eosinophil counts have not recovered (to normal range or baseline levels), the subject must return for Extended Follow-Up visits approximately every 28 days to monitor blood counts until lymphocyte and/or eosinophil counts have recovered. Extended Follow-Up visits will consist only of blood collection for CBC with differential and collection of any AESI and SAE.

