13.2 Serious Adverse Events

A serious adverse event (SAE) is defined as an AE that meets one of the following criteria:

- Death
- A life-threatening AE that places the subject at risk of death at the time of the event. It does not refer to an event that hypothetically might cause death if it were more severe.
- Inpatient hospitalization or prolongation of existing hospitalization.
- A persistent or significant disability/incapacity.
- A congenital anomaly/birth defect occurring in the offspring of a study subject.
- Other important medical events may also be considered an SAE when, based on appropriate medical judgment, they jeopardize the subject or require intervention to prevent one of the outcomes listed above.

SAE will be assessed and recorded after the first administration of study drug and ending at the time of the Day 197 visit, the Day 372 visit (for subjects participating in the OLE period), the ET visit, or the last Extended Follow-Up visit (if applicable), unless otherwise directed by Allakos. If an SAE that occurs during the screening period (after consent and before the first administration of study drug) is assessed to be related to a screening procedure, it will also be recorded.

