15.8 Safety Analysis

Adverse Events: All AE will be coded using the Medical Dictionary for Regulatory Activities (MedDRA) and will be classified by MedDRA system organ class (SOC) and preferred term. Listings will include all AE collected on study. The summaries of AE will be based on TEAE, defined as an AE reported in the clinical database with a date of onset (or worsening) on or after the start date of the first IV infusion of the study medication.

Subject incidence (N and %) of TEAE will be summarized as follows:

- Overview of TEAE will include:
 - Number (%) of subjects who reported at least 1 TEAE overall, by maximum severity, and by strongest relationship
 - Number (%) of subjects who reported at least 1 serious TEAE
 - Number (%) of subjects who reported at least 1 TEAE leading to treatment discontinuation
 - Number (%) of subjects who reported at least 1 TEAE leading to study discontinuation
 - Number (%) of subjects who reported at least 1 TEAE of special interest (TEAESI)
- TEAE by preferred term in descending order of subject incidence
- TEAE by SOC and preferred term
- TEAE by maximum severity, SOC, and preferred term
- Drug-related TEAE by SOC and preferred term
- TEAE leading to treatment discontinuation by SOC and preferred term
- Serious TEAE by SOC and preferred term
- TEAESI by SOC and preferred term

Clinical Laboratory Assessments: Descriptive statistics will be used to summarize hematology, chemistry, and urinalysis results at Baseline, each visit, and the change from Baseline for each visit. In addition, shift tables will summarize the laboratory results relative to normal reference ranges at Baseline and each post-baseline time point. Number (and %) of subject incidence of positive ADA tests will be summarized.

Vital Signs: Vital signs will be summarized at Baseline, each visit, and change from Baseline at each visit.

ECG: Subject incidence of the Investigator's overall assessment (normal, abnormal – not clinically significant, and abnormal – clinically significant) will be summarized.

Physical Exam: New or worsening symptoms in the symptom-directed physical exams will be included in the by-subject data listing.

Prior and Concomitant Medications: All medications (prior and concomitant) will be coded using the most current World Health Organization Drug Dictionary (WHODD). Prior and concomitant medications will be summarized with subject and percent incidence by Anatomical Therapeutic Chemical Class and preferred term.

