**Table 2 Terminology and Definitions cont.**

Terminology	Definition
Enrolled	Subject who is randomized to a treatment group.
CCI	: See Appendix 1 .
EREFS	EoE Endoscopic Reference Score: See Appendix 1 .
Newly Initiated Medication	Refers to any medication with start date $\geq$ Study Day 1.
Prior Medication	Medication collected on the Prior/Concomitant Medication CRF with start date prior to Study Day 1.
PRO TSS	Total Symptom Score is the sum of 6 weekly average symptom intensity scores (abdominal pain, abdominal cramping, bloating, nausea, early satiety, and loss of appetite).
TEAE	Treatment-emergent adverse events reported in the clinical database with a date of onset on or after the start date of the first dose of the study drug.
Tissue Eosinophil Responder	For subjects who achieve a peak esophageal intraepithelial count of $\leq 6$ eosinophils/hpf at Week 24
Treatment Responder	Subjects who achieve a peak esophageal intraepithelial count of $\leq 6$ eosinophils/hpf at Week 24 and achieve $>30\%$ reduction in biweekly DSQ score at Weeks 23–24.
Study Day	Study Day 1 is defined as the date on which a subject took the first dose of Study Drug. Other study days are defined relative to Study Day 1. For visits prior to the first dose of Study Drug, Study Day is calculated as Visit Date – Day 1 Date. For visits after the first dose, Study Day is calculated as Visit Date – Day 1 Date +1.
Study Drug	AK002 or placebo administered by IV infusion.
Study Week	Defined as 7 days a week starting from the day of first dose (Day 1).

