### 5.6 Timing of Final Analyses

There will be 2 database locks for this study:

- A provisional database lock after all patients complete the Day 169 visit to allow for the analysis of safety and efficacy data through Day 169.
- A final database lock after all patients complete the study to allow for the analysis of any safety data collected after Day 169.

For each database lock, applicable EDC data will be locked in order to protect write access after the following preconditions are fulfilled:

- All records are entered in the database.
- All AE are coded to the satisfaction of the Chief Medical Officer.
- All medications are coded to the satisfaction of the Chief Medical Officer.
- All data queries have been resolved.
- All decisions have been made regarding all protocol violations and ITT population exclusions.
- Written authorizations to lock the database are obtained from Allakos Clinical Data Management and the Chief Medical Officer.

The randomization code for this study will not be revealed until the previous preconditions are fulfilled and documentation of the provisional database lock is complete. After the provisional database lock, the randomization code will be made available to a restricted number of individuals at Allakos who are involved in the analysis of data. Data analysis will commence after the provisional data lock and the final database lock, respectively. In addition, the PK and ADA data may be locked and assessed separately.

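### SAE and AESI collection continues past Day 197 or early termination only while blood counts are unrecovered, yet the TEAE period has no end and the final by-arm tables carry no time at risk

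*SAP*

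**What the plan says.** **TEAE period.** SAP Table 2 counts an event "reported in the clinical database with a date of onset on or after the start date of the first dose of the study drug". Protocol 15.8 uses an onset rule of the same kind, "with a date of onset (or worsening) on or after the start date of the first IV infusion of the study medication". Neither gives a last date. The Synopsis (Safety Evaluations) does say that TEAE are collected through Day 197, Day 372 for open-label (OLE) subjects, or early termination (ET). The SAP does not carry that limit over, and it states that it supersedes the protocol's statistical methods.

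**Extended follow-up.** Under Table 1 Note 33 and Protocol 11.2.8, a subject whose lymphocyte and/or eosinophil count has not returned to normal range or baseline by Day 197 or ET comes back about every 28 days until it does. No maximum is stated. The Synopsis adds: "During the period of extended follow-up, data collection will be limited to hematology, serious adverse events, and adverse events of special interest". Protocol 13.2 accordingly lets SAE recording run to Day 197, Day 372, "the ET visit, or the last Extended Follow-Up visit (if applicable"; 13.3 and 13.7.4 do the same for AESI. On the trigger itself, Protocol 11.2.8 says "expected effects of AK002 include changes in absolute lymphocyte and eosinophil counts".

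**Analysis.** SAP 5.6 plans a provisional lock for data through Day 169 and a final lock "to allow for the analysis of any safety data collected after Day 169". SAP 6.15.1 reports TEAE, including serious TEAE and TEAESI (Tables 14.3.1.7 and 14.3.1.8), as n and % of subjects. The only duration summary, in SAP 6.10.1, is last dose date minus first dose date plus 1.

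**Follow-up after stopping.** The Synopsis says "all subjects will be followed for 8 weeks after the last dose of study drug". Table 1 Note 32 and Protocol 12.13 set the ET visit at 28 (±3) "days after the last dose of study drug or prior to this, if necessary, to ensure compliance with the visit". Protocol 14.2 encourages subjects who stop study drug to stay and complete follow-up. SAP 4.2.5 mentions a 12-week follow-up period after withdrawal from treatment for prohibited medication.

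**The concern.** How long a subject is watched for serious and special-interest events depends on a laboratory result measured after randomisation, and the study drug is expected to change that result. If more AK002 than placebo subjects are unrecovered, AK002 subjects are observed longer on average. A crude percentage then rises on AK002 even if the true event rate is the same in every arm.

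The AESI list includes malignancy, parasitic infection and opportunistic infection, all of which can surface late. An imbalance of a few such events could be read as a drug signal when part of it comes from longer observation. With no time at risk in the tables, a reader could not separate the two.

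**Working it through.** **Step 1: the common window.** Last double-blind dose is Day 141 and end of study is Day 197: (197 − 141)/7 = 8.0 weeks. This reproduces the stated 8 weeks.

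**Step 2: do late events reach the final tables?** Protocol 14.1 records a non-OLE subject in extended follow-up as complete only at the last such visit. The final lock comes after all subjects complete and is made for safety data after Day 169. The SAP's TEAE rule has no end. An SAE or AESI with onset in extended follow-up therefore meets the SAP's definition. The Synopsis collection limit points the other way, so the documents leave the matter unsettled.

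**Step 3: who is affected?** OLE entrants leave the double-blind database at the first open-label infusion, about Day 176, in every arm. Non-entrants, including early terminators, are exposed to the extension.

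**Step 4: possible size.** Let u be the share entering the OLE (taken as equal across arms), q the share of non-entrants unrecovered, and k the number of 28-day extended visits. Counting from Day 1, observation is 176 − 1 = 175 days for OLE entrants and 197 − 1 = 196 days for others before any extension:

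mean days = u × 175 + (1 − u) × (196 + 28 × k × q)

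The documents give no q, k or u for this trial. Assumed: q = 0.50 to 1.00 on AK002 and 0 to 0.05 on placebo; k = 1 to 6; u = 0, 0.5 and 0.9. The only uptake figure in the documents is above 90%, from the Phase 2 study in a different disease.

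| u | Low case (q 0.50 vs 0.05, k = 1): days, ratio | High case (q 1.00 vs 0, k = 6): days, ratio |
|---|---|---|
| 0 | 210.0 vs 197.4, 1.06 | 364.0 vs 196.0, 1.86 |
| 0.5 | 192.5 vs 186.2, 1.03 | 269.5 vs 185.5, 1.45 |
| 0.9 | 178.5 vs 177.2, 1.01 | 193.9 vs 177.1, 1.10 |

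**Step 5: effect on a crude percentage.** Take q = 0.80 vs 0.05, k = 3 and an assumed identical true rate of 10 events per 100 person-years, with each subject's risk equal to 1 − exp(−rate × time).
- u = 0: 263.2 vs 200.2 days (ratio 1.31), crude incidence 6.95% vs 5.33%.
- u = 0.9: 183.8 vs 177.5 days (ratio 1.04), crude incidence 4.91% vs 4.74%.

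If both arms trigger equally (0.05 vs 0.05), every ratio is 1.00.

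**Step 6: early terminators.** The formula treats all non-entrants as reaching Day 197. An early terminator with recovered counts is seen for about 4 weeks after the last dose. One with unrecovered counts is seen for 4 + 4k weeks, which is 8 to 28 weeks for k = 1 to 6. The documents do not say how many there will be.

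**The case against.** Several points on the other side stand.

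- The Synopsis limits TEAE collection to Day 197, Day 372 or ET and then treats extended follow-up separately. The sponsor may intend that limit, in which case the fault is that the SAP omits it.
- The provisional analysis through Day 169 has a common planned window, and completers have no extended follow-up before then.
- Safety tables carry no formal inference (Protocol 15.1), and all AE are listed with onset day, so late events can be identified.
- Infusion-related reactions, the most common TEAE so far, must occur within 24 hours of infusion start (Protocol 13.4) and so cannot arise in extended follow-up. Events that are neither serious nor AESI are not collected there.
- Any distortion makes AK002 look less safe, which some would call conservative. A spurious malignancy or infection imbalance would still misinform.

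A reader might go further and infer that the extra period falls almost wholly on AK002, that late placebo events are never recorded, and that nothing can be done afterwards. The documents do not support this. The trigger applies to every arm, so an unrecovered placebo subject is followed too. Past studies describe lymphocytes recovering within 24 hours, so eosinophils would drive the trigger, but neither their recovery by Day 197 nor the laboratory's lower limit is given. If that limit were zero (an assumption), depleted subjects could count as within normal range and the extension would seldom start. Truncating on onset date would restore a common window.

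It is also tempting to quote 1.14, 1.43 or 1.86 for 4, 12 or 24 extra weeks. Those figures need every AK002 subject and no placebo subject to trigger, with nobody entering the OLE.

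**Conclusion.** The point holds in a limited form. As written, the rules make SAE and AESI observation depend on a result that AK002 is expected to change, and the SAP neither ends the TEAE period nor accounts for time at risk. The likely direction is inflation of late events on AK002, provided the trigger fires more often there.

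The size is uncertain: observation-time ratios of 1.01 to 1.86 over the assumed range, and no more than about 1.10 if OLE entry reaches 90%. The effect is confined to the final-lock SAE and AESI tables and to subjects who do not enter the OLE. It leaves the Day 169 analysis of completers untouched. The change should be made before unblinding because it is cheap; nothing here suggests that the safety data would be unusable without it.

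**What to change.** 1. **End the TEAE period.** In SAP Table 2 and 6.15.1, close the period used for between-arm tables at the Day 197 visit (including its window), the ET visit, or the first open-label infusion, whichever comes first. This follows the Synopsis collection rule. Tying the end to the visit avoids losing events collected at a Day 197 visit held late. The window itself needs settling: the Synopsis gives ±3 days and Table 1 gives ±7. Report SAE and AESI from extended follow-up in a separate, labelled summary and listing so that none is lost. The term 28 × k × q then drops out of the main tables: planned mean observation is 196, 185.5 or 177.1 days at u = 0, 0.5 or 0.9 in every arm, a ratio of 1.00 if OLE entry is equal.
2. **Add rates.** Give SAE and AESI rates per subject-year of observation by arm, using total observation time as well as the dosing interval in SAP 6.10.1. This also deals with any difference between arms in early termination or OLE entry, which a common end point alone does not.
3. **Reconcile the follow-up durations** in the Synopsis, Table 1 Note 32, Protocol 12.13, Protocol 14.2 and SAP 4.2.5. Which duration applies is for the sponsor to decide.

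**Cost:** SAP wording, one date flag, one or two added tables, and a wording change to align the follow-up texts. The small downside is that late SAE and AESI appear beside the main incidence table and not within it.

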## 4.2 Target of Estimation

The estimand (target of estimation) for Protocol AK002-014 is:

*In subjects with active EoE, what is between group (AK002 vs. Placebo) difference in the proportion of tissue eosinophil responders at Week 24, and group difference in biweekly DSQ from baseline to Weeks 23–24 as measured by the patient reported Dysphagia Symptom Questionnaire.*

The sections below describe the attributes of the estimand consistent with the ICH E9 (R1) Addendum ([FDA, 2021](#)).

### 4.2.1 Population Targeted by the Scientific Question

The population targeted by the scientific question is defined by the inclusion and exclusion criteria as part of the study protocol. Subjects must have a clinical diagnosis of active EoE.

